14.2 Recruitment rates

A total of 356 participants will be recruited at an expected rate of 2.5 participants per site per year. Recruitment rates will be monitored via several stop/go decision time points outlined in section 14.1 and review by the TMG, IDMC, and TSC at each meeting. The internal pilot will comprise of the first 50 patients recruited.

15 Pharmacovigilance

The Principal Investigator is responsible for ensuring that all site staff involved in this trial are familiar with the content of this section.

All SAEs must be reported immediately (and within 24 hours of knowledge of the event) by the PI at the participating site to the CTR PV and Safety Specialist unless the SAE is specified as not requiring immediate reporting (see section 15.3). This includes SAEs related to IMPs and non-Investigational Medicinal Products (nIMPs).

15.2 Definitions

Term	Definition
Adverse Event (AE)	Any untoward medical occurrence in a participant or clinical trial participant administered a medicinal product and which are not necessarily caused by or related to that product
Adverse Reaction (AR)	Any untoward and unintended response in a clinical trial participant to an investigational medicinal product which is related to any dose administered to that participant

Serious Adverse Event	Any adverse event that -							
(SAE)	Results in death							
	 Is life-threatening* 							
	 Required hospitalisation or prolongation of existing hospitalisation** 							
	Results in persistent or significant disability or incapacity							
	 Consists of a congenital anomaly or birth defect 							
	Other medically important condition***							
Serious Adverse Reactions (SARs)	Any SAE occurring in a clinical trial participant for which there is a reasonable possibility that it is related to the IMP at any dose administered.							
Suspected Unexpected Serious Adverse Reactions (SUSARs)	A SAR, the nature and severity of which is not consistent with the Reference Safety Information (RSI) for the IMP.							

^{*}Note: The term 'life-threatening' in the definition of serious refers to an event in which the trial participant was at risk of death at the time of the event or it is suspected that used or continued used of the product would result in the subjects death; it does not refer to an event which hypothetically might have caused death if it were more severe.

15.3 Trial Specific SAE Reporting requirements

In addition to the SAE reporting requirements above, for the purposes of this trial the following events will also be considered SAEs and must be captured on the SAE form and reported to the CTR with 24 hours of knowledge of the event:

- Opportunistic Infections (all grades)
- Unexpected or severe neuropsychiatric events (all grades)

For the purposes of this trial the following events will not require reporting as SAEs because they are anticipated events. They must be recorded on the appropriate CRF. If causality is suspected, they must be reported in the usual SAE time frames:

Death due to disease progression

These should be completed in the participant's notes and on the relevant toxicities CRF page and forwarded to the CTR in the normal timeframes for CRFs.

15.4 Causality

Causal relationship will be assessed for IMPs, other trial treatments (nIMPs) and procedures:

^{**} Note: Hospitalisation is defined as an inpatient admission, regardless of the length of stay, even if the hospitalisation is a precautionary measure for continued observation. Pre-planned hospitalisation e.g. for pre-existing conditions which have not worsened, or elective procedures, does not constitute an SAE.

^{***} Note: other events that may not result in death, are not life-threatening, or do not require hospitalisation, may be considered as an SAE when, based upon appropriate medical judgement, the event may jeopardise the participant and may require medical or surgical intervention to prevent one of the outcomes listed above.

IMPs: IVIG

nIMPs: methylprednisolone, Oral prednisolone

The Principal Investigator (or another delegated medically qualified doctor from the trial team) and Chief Investigator (or another medically qualified doctor from the Trial Management Group) will assess each SAE to determine the causal relationship based on the assumption that the participant received the IMP:

Relationship	Description	Reasonable possibility that the SAE may have been caused by the IMP?
Unrelated	There is no evidence of any causal relationship with the trial/intervention	No
Unlikely	There is little evidence to suggest there is a causal relationship with the trial/intervention (e.g. the event did not occur within a reasonable time after administration of the trial medication). There is another reasonable explanation for the event (e.g. the participant's clinical condition, other concomitant treatment).	No
Possible	There is some evidence to suggest a causal relationship with the trial/intervention (e.g. because the event occurs within a reasonable time after administration of the trial medication). However, the influence of other factors may have contributed to the event (e.g. the participant's clinical condition, other concomitant treatments).	Yes
Probable	There is evidence to suggest a causal relationship and the influence of other factors is unlikely.	Yes
Definite	There is clear evidence to suggest a causal relationship and other possible contributing factors can be ruled out.	Yes

The causality assessment given by the Principal Investigator (or delegate) cannot be downgraded by the Chief Investigator (or delegate), and in the case of disagreement both opinions will be provided.

15.5 Expectedness

The Chief Investigator (or another delegated appropriately qualified individual) will assess each SAR to perform the assessment of expectedness.

The expectedness assessment should be made with reference to the current Reference Safety Information (RSI) for each IMP. Expectedness decisions must be based purely on the content of the

RSI; other factors such as the participant population and participant history should not be taken into account. Expectedness is not related to what is an anticipated event within a particular disease.

SARs which add significant information on specificity or severity of a known, already documented adverse event constitute unexpected events. For example, an event more specific or more severe than that described in the RSI is considered unexpected.

The table below lists the RSIs that should be referenced.

IMP	RSI to be used for expectedness assessment	Relevant section to be used for expectedness assessment
Gamunex	Summary of Product Characteristics	Section 4.8
	10g/100ml vials	

Reference Safety Information (RSI) on any CTR trial will be reviewed regularly according to CTR procedures.

15.6 Reporting procedures

15.6.1 Participating Site Responsibilities

The PI (or delegated medically qualified doctor from the trial team) should sign and date the SAE CRF to acknowledge that he/she has performed the seriousness and causality assessments. Investigators should also report SAEs to their own health boards or trust in accordance with local practice.

A completed SAE form for all events requiring immediate reporting should be submitted via email to the CTR within 24 hours of knowledge of the event. A separate form must be used to report each event, irrespective of whether or not the events had the same date of onset.

The participant will be identified only by trial number, date of birth and initials. The participant's name should not be used on any correspondence.

It is also required that sites respond to and clarify any queries raised on any reported SAEs and report any additional information as and when it becomes available through to the resolution of the event. Additionally, CTR may request additional information relating to any SAEs/SARs and the site should provide as much information as is available to them in order to resolve these queries.

Serious Adverse Event (SAE) email address:

[contact]

SAE [contact]

Serious adverse events should be reported from time of signature of informed consent, throughout the treatment period up to, and including 3 months post randomisation. Serious adverse reactions (such as long term side effects of trial treatment under investigation) should continue to be reported until the end of follow up.

Adverse events (AE) should be graded using the NCI Common Terminology Criteria for Adverse Events (CTCAE) Version 5.0. The toxicity grades should be recorded on the toxicity part of the CRF.

An SAE form is not considered as complete unless the following details are provided:

- Full participant trial number, and either Initials or DOB
- An Adverse Event / Adverse Reaction
- A completed assessment of the seriousness, and causality as performed by the PI (or another appropriately medically qualified doctor registered on the delegation log).

If any of these details are missing, the site will be contacted and the information must be provided by the site to the CTR within 24 hours.

All other AEs should be reported on the CRF following the CRF procedure described in Section 18.1

15.6.2 The CTR responsibilities

Following the initial report, all SAEs should be followed up to resolution wherever possible, and further information may be requested by the CTR. Follow-up information must be provided on a new SAE form.

The CTR should continue reporting SAEs until 3 months post randomisation. Serious adverse reactions should continue to be reported until the end of follow-up.

Once an SAE is received at the CTR, it will be evaluated by staff at the CTR and sent to the Chief Investigator (or their delegate) for an assessment of expectedness.

Investigator reports of suspected SARs will be reviewed immediately and those that are identified as SUSARs are reported to the MHRA, and Main Ethics Committee.

15.7 SUSAR reporting

University of Liverpool is undertaking the duties of trial Sponsor and has delegated to the CTR the responsibility for reporting SUSARs and other SARs to the regulatory authorities (MHRA and relevant ethics committees):

SUSARs which are fatal or life-threatening must be reported to the MHRA and REC within 7 calendar days of receipt at the CTR. If report is incomplete then additional follow-up information should be reported within a further 8 calendar days of submitting the initial report.

SUSARs that are not fatal or life-threatening must be reported to the MHRA and REC within 15 days of receipt at the CTR. Any additional, relevant information must be reported within a further 15 days.

N.B. There is no requirement for the CTR to report SUSARs to nIMPs to the MHRA except in the following instances:

- If the adverse reaction is suspected to be linked to an interaction between a nIMP and IMP, and is serious and unexpected, CTR should report as a SUSAR due to the interaction with the IMP.
- If a SUSAR is suspected and might be linked to either a nIMP or an IMP and cannot be attributed to only one of these.
- If the adverse reaction due to the nIMP is likely to affect the safety of trial subjects then CTR should report it to the MHRA and REC in accordance with the relevant Standard Operating Procedure for reporting Urgent Safety Measures.

15.8 Unblinding for the purposes of SUSAR reporting

To enable processing of a SAR in this blinded trial, expectedness should be assessed initially using the assumption that the IMP has been given to the trial participant.

If it is assessed as unexpected as per the RSI of the IMP, the SUSAR will be unblinded by the CTR safety group prior to reporting to the MHRA and REC.

If after unblinding, it is evident that the trial participant received the placebo, this event will not require expedited reporting to the MHRA and REC, unless in the opinion of the Principal Investigator or Chief Investigator the event was related to the placebo (for example an allergic reaction to an excipient).

15.9 Safety Reports

A list of all SARs (expected and unexpected) will be reported annually to the MHRA, REC, and trial sponsor in the form of a Development Safety Update Report (DSUR). This report must be submitted within 60 days of the anniversary of the MHRA CTA approval date.

The CTR will report a list of all SARs (expected and unexpected) and any other safety recommendations to all PIs once a year throughout the course of the trial. This frequency may be reviewed and amended as necessary. The reporting frequency and changes will be fully document in the Enceph-IG risk assessment. This reporting will be done via the Investigator safety report (ISR).

15.10 Pregnancy

15.10.1 Pregnancy reporting whilst participating in the trial

Pregnancy, or the pregnancy of a partner occurring whilst participating in the trial, is not considered an SAE, however, a congenital anomaly or birth defect is. Other cases (e.g. termination of pregnancy without information on congenital malformation, and reports of pregnancy exposure without outcome data) should not normally be reported as such. When pregnancy occurs in a trial, either in a female participant or the female partner of a male participant, this should be followed up until at least the end of pregnancy, whether that is a live birth, abortion etc. Without follow-up of the pregnancy, it would not be possible for the CTR to know if a congenital anomaly or birth defect occurred, and therefore if there was an SAE that must be included in the safety evaluation of the IMP. Information on a pregnancy in a trial participant will be captured on the CTR Pregnancy Report Form supplied to sites by the CTR.

Sites should report pregnancy occurring within SAE reporting periods stipulated in the trial protocol (for example, some trial protocols may state that SAEs should be reported during the trial treatment period and up to 30 days after the last date of treatment, this timeline would also apply to the reporting of pregnancies). Congenital anomalies or birth defects are considered an SAE and so these events must also be reported to the CTR on a trial-specific SAE form. Congenital anomalies or birth defects related to the IMP and unexpected with respect to the IMP Reference Safety Information (RSI) must be submitted by the CTR within expedited SUSAR time frames (7 or 15 days) to the MHRA, relevant REC and the drug manufacturer of the IMP (to comply with any contractual agreement).

15.11 Urgent Safety Measures (USMs)

An urgent safety measure is an action that the Sponsor, Chief Investigator or Principal Investigator may carry out in order to protect the subjects of a study against any immediate hazard to their health or safety. Any urgent safety measure relating to this study must be notified to the Research Ethics Committee immediately by telephone, and in any event within 3 days in writing, that such a measure has been taken. USMs reported to the CTR will be handled according to CTR processes.

16 Statistical considerations

16.1 Randomisation

Patients will be randomised 1:1 to IVIG or placebo using random permuted blocks stratified by site, and time from symptom onset. The final randomisation lists, which will contain investigational medicinal product identifications and corresponding allocations (IVIG / placebo), will be generated by a statistician otherwise not involved in the trial and will be supplied to the manufacturing and site pharmacy for appropriate labelling, as well as the CTR safety team. Randomisation will take place online using Vanilla, a system created by the CTR. It will be available 24 hours a day. On randomisation, a participant will be allocated to the next available treatment. The research team, treating healthcare professionals, participants and their families will remain blind to allocated treatment for the duration of the study.

16.2 Blinding

This will be a multicentre double-blind two-arm placebo-controlled randomised trial of IVIG in adults with autoimmune encephalitis. Patients, family, health care workers and study team will be blinded to protect against performance and ascertainment bias. There will be no planned unblinding while the trial is ongoing.

Blinding information (i.e. codes corresponding to IVIG/placebo allocations) will be held by:

- Manufacturing Pharmacy Unit
- The Pharmacovigilance team at the Centre for Trials Research, Cardiff University;
- A study-independent statistician at the Centre for Trials Research, Cardiff University.

Final unblinding prior to statistical analysis

The statistician responsible for conducting the final statistical analysis will be unblinded following database lock, data cleaning, and derivation of variables required to perform analysis has taken place.

Unblinding for analysis to be reported at IDMC meetings

Statistical analyses for IDMCs which require reporting of data by trial arm or for one arm only (e.g. as proposed for the internal pilot) will be prepared by a study-independent statistician.

Emergency unblinding

Unblinding will only occur in situations in which it is critical for the clinical management of the patient. In the cases of an SAE, the reporting clinician should treat the participant as if they had received the IMP. In the event of a SUSAR, the CTR safety team will be able to break the blind.

Site PI or appropriately delegated individual (listed in delegation log) is responsible for making decisions regarding emergency unblinding.

The following procedure should be followed in all instances of unblinding:

- 1. A web-based unblinding system will be made available to the local investigational team. Access will be controlled using a unique username and password.
- 2. An authorised member of the investigational team will log on to the unblinding system. On entering the required information, including the Pack ID of the participant, the treatment allocation will be revealed. The allocation will be transmitted to the person primarily responsible for their care.
- 3. A delegated member of the research team will complete the Enceph-IG Unblinding CRF, to be returned to the CTR within 24 hours of the event.
- 4. The trial treatment allocation should not be included on the CRF and the allocation should not routinely be revealed to CTR staff.

In the event sites are not able to access the randomisation system, sites can contact their local pharmacy or, the CTR safety team (during office hours), who will arrange for unblinding to be performed by accessing the online system or using the hardcopy master randomisation list.

16.3 Sample size

We will require 356 participants in total (178 per arm). This is based on a two-sided alpha of 0.05, 85% power, and a median time to recovery in our placebo arm of 87 days (based on analysis of patients in the Enceph-UK study) with 20% of participants not having recovered by the 12-month follow-up period for the primary outcome), and a hazard ratio of 1.43 (i.e. a 30% relative improvement in the median

time to recovery – translating into an absolute difference of 26 days). Our extensive discussions with doctors, patients and their families indicated that this would be considered a clinically significant improvement in recovery time. There are considerable data in autoimmune and other forms of encephalitis that early recovery leads to better outcomes overall (Ooi et al., 2008; Raschilas et al., 2002; Titulaer et al., 2013); for example, in a retrospective study of 577 patients with anti-NMDA receptor encephalitis, patients who responded to first line immunotherapy had a better outcome at 24 months than those who did not respond and required second line therapy (Titulaer et al., 2013). In our unpublished analysis of Enceph-UK data, 80% of autoimmune encephalitis patients had recovered (as assessed by GOSE ≥5) within 12-months, which is comparable to published series (Titulaer et al., 2013). Our sample size is inflated to account for 5% drop-out. As our outcome is time-to-event based, and participation in the trial following the initial five-day treatment period revolves around providing follow-up data, we expect drop-out and missing data to be low.

As a secondary outcome, our study will be able to detect a difference in the proportion of patients with a GOSE of 5 or more at 3 months follow up from 0.5 (based on our Enceph-UK data) to 0.67 (i.e. 34% relative difference); this is based on the sample size of 354 (allowing for 15% loss to follow up), two-sided alpha of 0.05, and 85% power. At 12 months, we will be able to detect a difference in the proportion of patients with a GOSE of 5 or more from 0.8 (based on our Enceph-UK data) to 0.94 (i.e 17.5% relative difference); this is based on the sample size of 244 (allowing for 15% loss to follow up) two-sided alpha of 0.05, and 85% power. We expect 30% of patients to be antibody positive, and within this subgroup (approximate 106 patients) we will have approximately 80% power to detect a hazard ratio of 1.84. This translates into a 46% relative improvement in the median time to recovery for patients allocated to IVIG, or an absolute difference of 40 days (i.e. from 87 to 47 days).

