13.2 Follow-up

Data collection will continue for all patients until 3 months after the last patient is recruited. The primary outcome measure will be collected fortnightly for the first 3 months for all participants, and then monthly until 12 months post-randomisation for a subset of participants, unless participant reaches primary endpoint. A subset of participants will also complete the GOSE annually until the end of the trial. Clinical follow up assessments and assessments of self-rated health will be completed at 3 month for all participants, and then at 12 months and annually for a subset of participants. Participants recruited after month 45 of recruitment, will complete all assessments up to and including the 3 month assessment. Patients recruited up until month 44 of recruitment will complete all assessments up to and including the 12 month assessment, patients recruited up until month 32 of recruitment will complete all assessments up to and including the 36 month assessment. Those patients recruited up to month 8 of recruitment will complete all assessments up to and including the 48 month assessment. A detailed schedule of the assessments can be found in figure 3 in section 13.1.

For the fortnightly assessments, the follow up window is ±2 days. Participants will be notified 1 day before the follow up window starts and then again on the first day of the follow up window. If the participant does not complete the assessment on the first day, they will be contacted every day until they complete the assessment or the follow up window closes. For the monthly assessment, the follow up window is ±7 days. The same procedure will be used, except if participant doesn't complete the assessment on day 1 of the follow up window, they will be contacted every other day until the window closes. Any assessments that require in person attendance must be scheduled within the appropriate follow up window. Participants will be contacted at each assessment time point regardless of whether they completed the previous assessment point unless they withdraw their consent to take part in that section of the trial or the trial as a whole.

14 Internal pilot and recruitment rates

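### The 85% power in section 16.3 assumes 12-month follow-up for everyone; if the 3-month stop for late recruits in section 13.2 applies, power is about 81 to 82%

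*Protocol*

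**What the plan says.** Section 16.3 requires 356 participants. "This is based on a two-sided alpha of 0.05, 85% power, and a median time to recovery in our placebo arm of 87 days", "with 20% of participants not having recovered by the 12-month follow-up", with a hazard ratio of 1.43. The only inflation it mentions is 5% drop-out. For the secondary comparison of proportions it takes a placebo recovery of 0.5 at 3 months, and at 12 months "this is based on the sample size of 244 (allowing for 15% loss to follow up").

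Section 13.2 opens with "Data collection will continue for all patients until 3 months after the last patient is recruited". It then says that the primary outcome is collected monthly to 12 months only for a subset: those recruited up to month 44 go to 12 months, and "Participants recruited after month 45 of recruitment, will complete all assessments up to and including the 3 month assessment". The same paragraph sets annual cut-offs, among them "patients recruited up until month 32 of recruitment will complete all assessments up to and including the 36 month assessment", and month 8 for 48 months.

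Sections 5.3 and 13.1 schedule GOSE fortnightly for 3 months and then monthly to 12 months or until the endpoint, with no restriction by recruitment date. The primary analysis in section 17.1 refers to the section 5.3 schedule. The opening of section 13 says that the number of monthly follow-ups depends on when a participant is recruited. Section 16.4 censors at the last time with data.

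**The concern.** The sample size rests on the share of participants who have recovered by 12 months. If the trial deliberately stops measuring a sizeable group at 3 months, when only about half of the placebo arm is expected to have recovered, the expected number of events is lower than the calculation assumes. Section 16.3 recognises the reduced 12-month number for a secondary outcome but not for the primary one.

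What is at stake is the power of the primary analysis, and whether sites know how long to collect the primary outcome in late recruits. Bias and type I error are not at stake: planned administrative censoring is handled properly by Cox regression.

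**Working it through.** **Inputs (section 16.3 unless noted).** Two-sided alpha 0.05; power 85%; hazard ratio 1.43; placebo unrecovered at 12 months 0.20; placebo recovered at 3 months 0.50; drop-out 5%; N = 356; 244 participants in the 12-month comparison.

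**Step 1: reproduce 356.**
- Events (Freedman): (1.960 + 1.036)² × (2.43/0.43)² = 287.
- Event probability at 12 months: placebo 0.80; IVIG under proportional hazards 1 − 0.20^1.43 = 0.900; mean 0.850.
- 287/0.850 = 338, and 338/0.95 = 356, the stated figure.
- Schoenfeld's formula gives 281 events and N = 349. Using 0.80 in both arms gives 370 (Schoenfeld) or 378 (Freedman).

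**Step 2: how many stop at 3 months.** Section 13.2 gives no count.
- 356 − 244 = 112. The 244 is a number before loss: 0.80 against 0.94 at 85% power needs 206, and 206/0.85 = 242.
- The cut-offs 44 + 12 and 8 + 48 both put the close at recruitment month 56, so the last recruit would enter at about month 53. That leaves about nine months of late recruitment. At the section 14.2 rate, 50 × 2.5/12 = 10.4 per month, giving about 94.
- Taking the section 14.1 target of 70 at month 24, and assuming even accrual to month 53: (356 − 70)/29 × 9 = about 89.

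**Step 3: events and power with the stop.** Event probability at 3 months: placebo 0.50; IVIG 1 − 0.50^1.43 = 0.629; mean 0.564. With 112 stopped, events = 0.95 × (244 × 0.850 + 112 × 0.564) = 257. Freedman power = Φ(√257 × 0.43/2.43 − 1.96) = 0.810.

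| Follow-up | Late recruits | Events | Freedman | Schoenfeld |
|---|---|---|---|---|
| All to 12 months | none | 287 | 85.1% | 85.8% |
| Stop at 3 months | 112 | 257 | 81.0% | 81.8% |
| Stop at 3 months | 94 | 262 | 81.7% | 82.5% |
| Stop at 3 months | 89 | 263 | 81.9% | 82.7% |
| Stop at 3 months, first qualifying score needed by week 10 | 112 | 249 | 79.7% | 80.6% |
| Common close, 3 to 11 months (assumed uniform) | 112 | 274 | 83.4% | 84.1% |

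The week-10 row reflects the two-in-a-row rule. A late recruit's last assessments are at week 10 and month 3, so a first score of 5 or more at month 3 cannot be confirmed.

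The common-close row assumes a piecewise constant hazard through 50% recovered at 87 days and 80% at 365 days. A log-rank simulation on the same curve (20,000 runs per scheme, late share 112/356) gave 85.6% with full follow-up, 82.3% with the stop, 80.1% with the week-10 limit and 84.7% with the common close.

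With 112 stopped, varying placebo recovery at 3 months from 0.45 to 0.55 moves Freedman power from 80.1% to 81.8%. Restoring 85% by numbers alone would need about 398 participants.

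**Step 4: antibody-positive subgroup (106 patients, hazard ratio 1.84, 5% drop-out).** Full 12-month follow-up gives 88 events and power of 79% (Freedman) or 82% (Schoenfeld), matching the stated figure of about 80%. With the stop, about 80 events give 75% or 78%.

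**Step 5: annual cut-offs.** Month 32 + 36 months = recruitment month 68. Section 14.1 equates recruitment month 6 with study month 16, so this is study month 78 of a 73-month trial, and 12 months after the month-56 close. Recruitment month 45 itself falls in neither the 12-month nor the 3-month group.

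**The case against.** The strongest reply is that the 3-month stop is not settled. The first sentence of section 13.2, the opening of section 13, and sections 5.3 and 13.1 can be read as staggered follow-up of everyone to a common close, and power would then be about 83 to 85%. That stands. A reader might infer that the trial simply has 81% power; the documents support this only if the explicit stop governs.

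The count of 112 is also an inference, and 89 to 94 is as defensible. That stands too, but it moves power by less than one percentage point.

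A reader might also infer that nearly a third of the primary data is thrown away. It is not. Late recruits contribute all data to 3 months, and regular GOSE ends at recovery anyway. About 112 × (1 − 0.564) = 49 participants, 14% of 356, would be unrecovered and lose later assessments, at a cost of about 0.95 × 112 × (0.850 − 0.564) = 30 events. Those data are not collected; none are discarded.

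One could argue that truncation was already built in: a constant hazard with an 87-day median and the 244/112 split gives N of about 358. But that hazard leaves only about 5% unrecovered at 12 months, against the stated 20%, so it is not the calculation that section 16.3 describes.

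Finally, the loss is modest and the hazard ratio and median are planning values. That bears on how serious the point is, not on whether the stated power matches the stated follow-up.

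**Conclusion.** The concern holds in conditional form. The stated 85% matches full 12-month follow-up, which section 13.2 does not provide. If the 3-month stop applies, expect about 257 to 263 events instead of 287 and power of about 81 to 82% (Freedman; up to about 83% by Schoenfeld), slightly lower once the confirmation rule is counted. If late recruits are followed to a common close, expect about 83 to 85%, depending on accrual after month 44, which the protocol does not give.

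These figures rest on proportional hazards, the protocol's own recovery proportions, 5% drop-out and the inferred number of late recruits. The trial remains viable. The protocol needs one consistent follow-up rule and a power statement that matches it. The month-32 cut-off is a separate error with no effect on primary power.

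**What to change.** 1. Reconcile section 13.2 with sections 5.3 and 13.1 so that one rule governs primary-outcome follow-up of late recruits. Preferably, continue the monthly online or telephone GOSE until confirmed recovery, 12 months or the common closing date, whichever comes first. Assign recruitment month 45 to a group.
2. In section 16.3, state the expected events and power for the chosen scheme, with the number of late recruits and the accrual assumption declared: about 81 to 82% if the 3-month stop is kept, about 83 to 85% under a common close.
3. Restate the antibody-subgroup power on the same basis (about 75 to 78% with 5% drop-out if the stop is kept).
4. Separately, correct the annual cut-offs so that cut-off plus follow-up equals the closing month. With a month-56 close, month 32 fits 24 months and month 20 fits 36 months.

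The cost is protocol wording and, under the preferred option, at most eight extra remote GOSE forms per unrecovered late recruit before the existing close. No extra participants or visits are needed. Keeping the stop is acceptable if section 16.3 states the lower power.
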